**A. SPECIFIC AIMS**

Polycystic ovary syndrome (PCOS) affects between 5 and 8% of women making it one of the most common endocrinopathies in women (3, 4). The disorder typically has its onset at puberty with evidence of excessive androgen production, obesity, and insulin resistance. Women with PCOS are more insulin resistant than weight-matched controls (5) and have an exceptionally high prevalence (6) of early-onset impaired glucose tolerance (30 - 40 percent), and type 2 diabetes (up to 10 percent) (7, 8). In addition, the rate of deterioration in glucose tolerance is accelerated in PCOS (7, 9). Vascular disorders are also common in this population due, at least in part, to disordered lipid metabolism. Hypertriglyceridemia, increased levels of very-low-density lipoprotein (VLDL) cholesterol, low-density lipoprotein (LDL) cholesterol, and decreased levels of high-density lipoprotein (HDL) cholesterol are typical (10) (11). While insulin resistance contributes to glucose intolerance and dyslipidemia, it has become increasingly clear that other factors must be involved in the pathogenesis of the metabolic derangements so commonly seen in PCOS.

Over the past several years, chronic decreases in sleep duration and/or quality have been identified as a risk for the development of a number of metabolic derangements (12-14) that are strikingly similar to those seen in PCOS (3, 10, 15). Specifically, decreased sleep quality due to obstructive sleep apnea (OSA) has been causally linked to insulin resistance, glucose intolerance, dyslipidemia and hypertension independent of body mass index (BMI) (12-14). Until recently however, it had not been recognized that **OSA is present in a disproportionate number of women with PCOS: the risk for OSA is at least 5-fold higher, and perhaps as much as thirty-fold higher (16), compared to the risk in similarly obese women without PCOS.**

It was initially thought that hyperandrogenemia or obesity are the key determinants of the high prevalence of OSA in PCOS. However, both published data (16) as well as results of our Preliminary Studies are not consistent with this hypothesis. We have found that plasma concentrations of free testosterone are virtually identical in PCOS women with and without OSA. In addition, measures of OSA severity, such as the apnea-hypopnea index (AHI), do not correlate with either the degree of androgen elevation or with body mass index (BMI) among PCOS women with OSA.

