Both progesterone and estrogen reportedly "protect" against the development of OSA (17, 18) (19-24) (25), and levels of these sex steroids are typically low in PCOS relative to those in normal cycling women. **Thus, we will test the hypothesis that circulating progesterone and estrogen levels are significant determinants in the development of OSA among hyperandrogenic women with PCOS. Using a novel paradigm that permits us to independently modulate sex steroid concentrations, we will be able to address the specific and independent effects of progesterone and estrogen in the pathogenesis of OSA among women with PCOS.**

OSA appears to be an underrecognized, yet significant factor in the pathogenesis of metabolic derangements in PCOS. In a recent study, we showed that measures of insulin resistance and glucose tolerance in PCOS women are strongly predicted by the severity of OSA (15). These intriguing findings suggest that there may be two "subtypes" of women with PCOS, i.e. those with and those without OSA, and that these two subtypes may be associated with distinct metabolic and endocrine alterations. PCOS women with OSA may be at much higher risk for diabetes and cardiovascular disease than PCOS women without OSA and may benefit from therapeutic interventions targeted to decrease the severity of OSA. **Thus, a major goal of the present project is to contrast the metabolic and hormonal features of these two subtypes of PCOS, explore causative mechanisms for the high prevalence of OSA in PCOS, and test the hypothesis that continuous positive airway pressure (CPAP) treatment may decrease the risk of diabetes and other cardiovascular and metabolic abnormalities in PCOS women with OSA.**

**Specific Aim 1. To determine if women with PCOS who have OSA differ from those without OSA as a consequence of differences in circulating concentrations of the sex-steroids estrogen and progesterone.** We hypothesize that in comparison to PCOS women without OSA, those who have OSA will have lower circulating levels of estradiol, progesterone, or both estradiol and progesterone at baseline. We will further test our hypothesis by comparing stimulated steroid levels in these two groups. Specifically,

we will compare the ovarian steroidogenic response to a single dose of the GnRH agonist leuprolide in PCOS women with and those without OSA. Developed by our group, the GnRH agonist test has become a novel method to assess ovarian steroidogenic function.

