#### C4. There is a 5-6 fold increase in risk for OSA in PCOS

We have obtained a polysomnogram and metabolic measures in 49 women with PCOS and 22 women without PCOS (Controls). Among the 22 Controls, 4 (18%) met criteria for OSA (using the most common AHI criterion of  $\geq 5$  events/hr of sleep). In contrast, 27 (55%) of 49 women with PCOS had OSA. The unadjusted odds ratio of 5.5 for OSA in PCOS is highly significant ( $p=0.006$ ; 95% CI 1.6 – 18.7). Even after adjustment for age and BMI, the odds ratio remains highly significant at 5.5 ( $p=0.009$ ; 95% CI 1.5 – 20.6). Within group comparisons are shown in Tables C4-1 and C4-2. The magnitude of metabolic abnormalities is greater in the presence of OSA as well. Control women with OSA had significantly higher diastolic blood pressure levels; 2hr glucose levels were also higher, but significance was lost after correction for multiple comparisons. PCOS women with OSA were significantly higher in age relative to those without OSA, but it is important to note that these women are only in their second and third decades of life. In addition, BMI and waist circumference were significantly higher in PCOS women with compared to those without OSA. As was the case in controls, 2hr glucose levels were also significantly higher, but significance was lost after correction for multiple comparisons. Finally, those with OSA had higher fasting insulin concentrations as well as higher levels of fasting triglycerides. Thus, in women with or without PCOS, the presence of OSA is associated with more profound metabolic abnormalities.

[figure not shown]
[figure not shown]
Table C4-1.

	Controls Without OSA	Controls With OSA	P- value*
n	18 (82%)	4 (18%)	
Age (yr)	29.9 $\pm$ 1.2	34.4 $\pm$ 1.9	0.123
BMI (kg/m  )	35.3 $\pm$ 1.5	40.7 $\pm$ 4.3	0.160
Waist Circ (cm)	97.1 $\pm$ 3.6	110.4 $\pm$ 8.6	0.123
Systolic BP (mmHg)	114.1 $\pm$ 3.3	134.0 $\pm$ 6.2	0.012
Diastolic BP (mmHg)	67.6 $\pm$ 1.9	80.3 $\pm$ 3.8	0.007*
Fasting glucose (mg/dl)	88.3 $\pm$ 2.2	94.9 $\pm$ 5.2	0.228
2hr glucose (mg/dl)	111.6 $\pm$ 6.5	151.6 $\pm$ 29.1	0.046
Fasting Insulin (pmol/L)	11.6 $\pm$ 1.7	11.8 $\pm$ 3.2	0.972
HOMA	0.4 $\pm$ 0.1	0.5 $\pm$ 0.1	0.877
A1C (%)	5.4 $\pm$ 0.1	5.8 $\pm$ 0.3	0.067
Cholesterol (mg/dl)	163.5 $\pm$ 6.4	172.0 $\pm$ 8.6	0.553
HDL (mg/dl)	54.8 $\pm$ 3.2	49.0 $\pm$ 5.3	0.417
Triglycerides (mg/dl)	76.2 $\pm$ 13.0	86.5 $\pm$ 9.2	0.712
LDL (mg/dl)	93.7 $\pm$ 6.5	105.5 $\pm$ 9.3	0.416

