## D2. Screening and Specific Aim 1 Procedures

46 subjects will need to be enrolled in Specific Aim 1 in order to ensure a sample size of 20 in the group of PCOS women without OSA; this figure of 46 subjects is based on an estimated 55% prevalence of OSA among PCOS women as shown in Preliminary Studies. This calculation accounts for the effects of expected dropouts from the study. The primary outcome measures for this Aim are the differences in progesterone and estrogen concentrations between groups.

[figure not shown]
Following an initial phone screening, eligible subjects will be admitted to the GCRC in the early evening and will undergo the following screening process as described in Figure D2-1, below.

**N.B. THE SCREENING PROTOCOL DETAILED BELOW WILL PERTAIN TO ALL SPECIFIC AIMS. BASED UPON THE RESULTS OF THIS SCREENING, SUBJECTS WILL BE CLASSIFIED AS EITHER OSA NEGATIVE, IN WHICH CASE THE**

EVALUATION IS COMPLETED, OR WILL BE CLASSIFIED AS **OSA POSITIVE**. OSA POSITIVE SUBJECTS WILL THEN BE GIVEN THE OPTION TO ENTER INTO THE PROTOCOLS DETAILED IN SPECIFIC AIM 2 OR SPECIFIC AIM 3. SUBJECTS WILL BE INFORMED THAT IF THEY CHOOSE TO CONTINUE INTO AIM 2 OR AIM 3, THEY WILL BE RANDOMLY ASSIGNED USING A RANDOMIZATION SCHEDULE PREPARED BY THE GCRC BIOSTATISTICIAN, DR. [name]. SUBJECTS RANDOMLY ASSIGNED TO SPECIFIC AIM 2 WILL ALSO BE INFORMED THAT FURTHER RANDOMIZATION WILL OCCUR TO ONE OF TWO TREATMENTS, AS DETAILED BELOW.

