### D3. Statistical Considerations

#### re: Specific Aim 1

With 20 subjects per group and assuming a two-sided alpha level of 0.05, there would be approximately 80% power to detect a 0.89 SD difference in progesterone or estrogen levels between PCOS women without and PCOS women with OSA. These values are derived from data obtained in a group of 10 PCOS women without OSA. Using the SD from the preliminary data, this study would be powered to detect a 42% difference in hormone levels between groups.

46 subjects will need to be enrolled for this Aim in order to ensure a sample size of 20 in the group of PCOS women without OSA; this figure of 46 subjects is based on an estimated 55% prevalence of OSA among PCOS women as shown in Preliminary Studies.

Progesterone and estrogen levels will be compared between the two groups using a two sample *t* test. A log transformation of the data will be performed if there is evidence of non-normality. Statistical correction will be made for multiple comparisons between groups.

#### re: Specific Aims 2 and 3

The PCOS women with OSA studied in Aim 1 plus additionally enrolled PCOS women with OSA (for a total of 60 subjects) will be randomized in a ratio of 2:1 to participate in Aim 2 (n=40) or Aim 3 (n=20). Block randomization will be performed using computer-generated random numbers.

#### • Specific Aim 2

For this Aim, there are three time points of interest: baseline (T1), six weeks after administration of depot leuprolide (T2), and at the end of study after receiving six weeks of either estrogen or progesterone

(T3). Treatment assignment to either estrogen (n=20) or progesterone (n=20) will be randomized using computer-generated random numbers.

If the variance in AHI is denoted by  $\sigma^2$  and the correlation between pre- and post-treatment AHI by  $r$ , then the variance of the change in AHI is given by  $2\sigma^2(1-r)$ . With 20 subjects per group and assuming a two-sided alpha level of 0.05, the **Table D3-1** below lists the difference in AHI change detectable between the two treatment groups with 80% power for varying values of  $r$ .

**Table D3-1. Difference in AHI change detectable between the two treatment groups with 80% power for varying values of  $r$ .**

$r$	Effect Size	Difference Detectable with $\sigma = 8$
0.25	$1.08\sigma$	8.6
0.50	$0.89\sigma$	7.1
0.75	$0.63\sigma$	5.0
0.90	$0.40\sigma$	3.2

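### Aim 1 compares hormone levels between OSA and non-OSA groups only by an unadjusted t test, so the result cannot be read as independent of BMI; a BMI-adjusted supportive model should be prespecified

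*Combined protocol and SAP*

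**What the plan says.** Section D2 names the endpoint: "The primary outcome measures for this Aim are the differences in progesterone and estrogen concentrations between groups". Section A gives the hypothesis that "those who have OSA will have lower circulating levels of estradiol, progesterone, or both estradiol and progesterone at baseline", with a further comparison of levels after a GnRH agonist.

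Section D3 (Statistical Considerations, re: Specific Aim 1) gives the analysis: "Progesterone and estrogen levels will be compared between the two groups using a two sample" t test, a log transformation if the data look non-normal, and a multiplicity correction whose method is not named. No covariate is listed. The covariates in Section D4 are hormone concentrations and belong to Aim 2 contingencies.

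Group membership comes from the screening polysomnogram: AHI above 15 for OSA, below 5 for no OSA (Section D2). Entry requires BMI of at least 30 (Section D1), with no upper limit and no matching by OSA status.

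On the preliminary data, Section C4 reports that "BMI and waist circumference were significantly higher in PCOS women with compared to those without OSA". For the PCOS-versus-control odds ratio the sponsor did adjust: "Even after adjustment for age and BMI, the odds ratio remains highly significant at 5.5".

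**The concern.** BMI differs by OSA status in the sponsor's own cohort, and Section B1 says OSA risk rises with fat mass. If BMI is also related to estrogen or progesterone within groups, the unadjusted difference mixes an OSA component with an adiposity component. A deficit could be hidden or produced, depending on the sign of that relation.

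This bears on how the result will be used. The title of Aim 1 is worded causally, and Sections A and B4 argue that obesity does not fully explain OSA in PCOS. A hormone difference between groups of unequal BMI, or the lack of one, neither supports nor refutes a reading that is independent of BMI. The plan has no analysis that addresses this.

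**Working it through.** **Inputs.** Table C4-2: BMI 35.2 ± 1.5 (SEM, n = 22) without OSA and 42.2 ± 1.1 (n = 27) with OSA. Section D3: 20 per group, two-sided alpha 0.05, effect 0.89 SD, equated to a 42% difference. Not in the documents: the within-group correlation between BMI and hormone level. It is assumed here at 0.1, 0.2 and 0.4, with either sign.

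**1. The plan's own figure.** The standard error of the difference is √(2/20) = 0.316 SD. Power for 0.89 SD is 80.4% by the normal approximation and 78.3% by the noncentral t (38 df). The stated figure of about 80% is reproduced.

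**2. The BMI gap.** SD = SEM × √n: 1.5 × √22 = 7.04 and 1.1 × √27 = 5.72, pooled 6.34. Gap = 7.0 / 6.34 = 1.10 SD. Truncating both normal distributions at 30 gives means 37.97 and 42.44 and SDs 5.23 and 5.45. The gap is then 4.46 / 5.34 = 0.84 SD. Table C4-2 split the women at AHI 5, while Aim 1 contrasts above 15 with below 5, so the gap in the trial is uncertain. The smaller value is used below.

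**3. Effect on the unadjusted t test.** Shift = 0.84 × correlation, that is 0.084, 0.168 and 0.336 SD. False support means a significant result in the hypothesised direction when there is no BMI-independent difference; its nominal rate is 2.5%.

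| Correlation (absolute) | BMI raises hormone: power for true 0.89 SD deficit | BMI raises hormone: false support | BMI lowers hormone: power | BMI lowers hormone: false support |
|---|---|---|---|---|
| 0 | 78% | 2.5% | 78% | 2.5% |
| 0.1 | 70% | 1.3% | 85% | 4.4% |
| 0.2 | 60% | 0.7% | 90% | 7.5% |
| 0.4 | 40% | 0.1% | 97% | 17.8% |

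On the plan's percent scale (42 / 0.89 = 47.2% per SD), a true 42% deficit appears on average as 34–26% in the first case and 50–58% in the second, for correlations 0.2–0.4.

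**4. What the BMI-adjusted model costs.** If BMI explains no hormone variance, the variance of the adjusted difference is multiplied by 1 + 0.84²/4 = 1.176. The standard error is 0.316 × √1.176 = 0.343 SD. With 37 df, power for 0.89 SD is 71.5%, and the 95% CI half-width is 2.026 × 0.343 = 0.69 SD, against 0.64 SD unadjusted. Averaging over random BMI imbalance instead of fixing it at 0.84 gives about 70% and 0.71 SD. In simulation at gap 0.84, the adjusted model rejects 2.5% in each direction under either sign, with power 72–78% at correlations 0.2–0.4.

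All power figures are before the planned multiplicity correction. Halving alpha for two hormones, for example, would take the unadjusted power to 68%.

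**The case against.** The strongest reply is that Aim 1 promises only a difference in levels, for which the t test is valid. Section A says that "we will be able to address the specific and independent effects of progesterone and estrogen in the pathogenesis of OSA", but ties this to the hormone manipulation, which is done in Aim 2. This stands, and it is why the t test should stay.

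Next, confounding needs a link between BMI and the hormone. The only link in the documents is positive and concerns estrone (Section B4), while the hypothesis names estradiol and progesterone. In Table C4-2 total and free testosterone differ by only −0.06 and 0.10 SD despite the full BMI gap. Testosterone is not the endpoint, so this evidence is indirect, but it counsels caution about size.

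The sponsor also notes that measures of OSA severity "do not correlate with either the degree of androgen elevation or with body mass index (BMI) among PCOS women with OSA". That concerns severity among women who all have OSA. Aim 1 contrasts presence with absence, where BMI did differ. It is, however, a reason not to assume that the wider AHI contrast enlarges the gap beyond 0.84 SD.

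Finally, adiposity may lie on the path from hormones to OSA, in which case adjustment removes part of a real effect. This stands: the two estimates answer different questions and both should be reported.

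A reader might also infer that age must be adjusted for, because "PCOS women with OSA were significantly higher in age relative to those without OSA". The documents support this less well. Section E excludes women over 40 to avoid age effects on ovarian steroidogenesis and, under Inclusion of Women, places those effects before 18 and after 40. Age is handled by restriction.

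**Conclusion.** The gap is real and worth repairing. Aim 1 compares non-randomised groups that probably differ in BMI, and the plan contains no BMI-adjusted analysis, so its result cannot be described as independent of adiposity.

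Three stronger readings are not supported. A reader might infer that the t test is the wrong test; it is right for the stated endpoint. A reader might infer that the design is biased towards the hypothesis; the sign is unknown, and if BMI raises the hormone, false support becomes rarer than nominal and the risk is a masked deficit. A reader might infer that adjustment would justify the causal wording of the aim; neither cross-sectional estimate establishes causation.

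The sizes rest on three assumptions: a BMI gap of 0.84 SD from truncated normals, 20 per group, and correlations of 0.2–0.4 that have no source in the documents. The imbalance in the preliminary data and the absence of an adjusted analysis do not depend on those assumptions. Confidence is medium, and the point is one that should be fixed.

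**What to change.** - Keep the two-sample t test as the unadjusted result.
- Prespecify beside it, as a key supportive analysis, a linear model of hormone level (log scale if needed) on OSA group with BMI as covariate, for baseline and for GnRH-agonist stimulated levels.
- Report both estimates with confidence intervals. Base any statement that a difference is independent of BMI on the adjusted model.
- State that adiposity may lie on the hormone-to-OSA path and that neither estimate establishes causation.
- State the lower precision: about 70% power for 0.89 SD and a 95% CI half-width of about 0.7 SD (roughly 33% on the plan's scale) if BMI explains no hormone variance, before multiplicity correction. A non-significant adjusted result must not be read as absence of a difference.

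Age may be added as an optional sensitivity analysis; it is not part of the required change.

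The cost is a few sentences of analysis text, since the BMI entry rule already requires BMI to be measured. The downside is the precision loss above. If BMI lowers the hormone, the adjusted model also gives up the inflated power of the unadjusted test (90–97% becomes 72–78%). For scale, about 25 per group would restore 80% power for the adjusted model at gap 0.84 and correlation 0, against 21 for the unadjusted t test. The sponsor should either accept and state the lower precision or revisit the sample size.

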**Specific Aim 2. To determine if OSA improves in women with PCOS treated with estrogen or progesterone.** For these studies, we will enroll women with PCOS who have OSA. Subjects will have a detailed baseline metabolic and metabolomic profile together with a baseline polysomnogram. Subjects will then receive a single dose of depot-leuprolide in order to suppress ovarian production of estrogen, progestin, and androgen over a period of 3 months. Six weeks after administration of depot-leuprolide, subjects will have repeated assessment of metabolic, metabolomic, and sleep measures to determine if these outcomes are altered by the combined suppression of ovarian sex steroids. Subsequently, subjects will be randomized in a double-blind placebo controlled fashion to one of two treatment arms for a period of six weeks. Treatment arms are: estrogen plus placebo or progesterone plus placebo. At the end of this second six weeks, subjects will have metabolic, metabolomic, and sleep measures repeated. Primary outcome measures will be compared both within and between treatment arms.

**Specific Aim 3. To determine if metabolic disturbances present in PCOS women with OSA are ameliorated by the treatment of OSA with continuous positive airway pressure (CPAP).** The presence of OSA in women with PCOS has a significant negative effect upon metabolic measures. In particular, the presence of OSA in PCOS is associated with hyperinsulinemia, elevations in plasma glucose, and lipid abnormalities that include higher levels of triglycerides and LDL-cholesterol. OSA in PCOS is also associated with hypercortisolemia that persists throughout both day and night. Results of our preliminary studies indicate that CPAP treatment of OSA results in attenuation of cortisol levels not only during sleep, but throughout waking hours as well. This aim will serve to test the hypothesis that correction of OSA in PCOS will lead to improved metabolic function which can be attributed, at least in part, to a reduction in circulating levels of cortisol.

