**At 15:50, a GnRH agonist test will be performed, as depicted in FIGURE D2-3 below.**

At 15:50, a 15cc blood sample for LH, FSH, estradiol, estrone, total and free testosterone, progesterone, 17-hydroxyprogesterone, and androstenedione will be obtained. At 15:59, a 5 cc blood sample will be taken for LH and FSH. At 16:00, leuprolide acetate 10 µg/kg will be given as a single subcutaneous injection. At 16:30, 17:00 and 20:00, 5 cc samples will be obtained for LH and FSH. A 15 cc sample will be obtained for estradiol, estrone, total and free testosterone, progesterone, 17-hydroxyprogesterone, and androstenedione after 16, 20, 24 hours GnRHa administration, i.e. at 8:00, 12:00 and 16:00.

As depicted in Figure D1-1, it is at this point that subjects will have completed the Screening and Specific Aim 1 Procedures. Details of procedures for subjects randomized into Specific Aim 2 or Specific Aim 3 are provided below.

### D3. Detail of methods pertaining to Specific Aims 2 and 3

The PCOS women with OSA studied in Aim 1 plus additionally enrolled PCOS women with OSA (for a total of 60 subjects) will be randomized in a ratio of 2:1 to participate in Aim 2 (n=40) or Aim 3 (n=20). Block randomization will be performed using computer-generated random numbers. The primary outcomes measure for Aim 2 is the AHI difference pre- and post-interventions, as detail in Section D3; the primary outcomes measure for Aim 3 is the change in 24 hr cortisol concentration pre- vs post-CPAP

Subjects randomized to Specific Aim 2 will have suppression of endogenous LH secretion, and thus ovarian sex-steroid production, by administration of a single intramuscular dose (11.25 mg) of the GnRH agonist depot leuprolide. Leuprolide is a synthetic nonapeptide analog of naturally occurring gonadotropin-releasing hormone (GnRH). The analog possesses greater potency than the natural hormone. When the depot form of leuprolide is administered at a dose of 11.25 mg, there is prolonged (3 month) suppression of pituitary gonadotropin levels and ovarian steroid levels as documented in the literature (115) and exemplified in Preliminary Studies. Six-weeks after administration, subjects will return to the GCRC for repeated evaluation, identical to that conducted at Baseline under Specific Aim 1.

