After this midpoint assessment, subjects will again enter into a randomized phase of the protocol. Subjects will be assigned to receive one of two treatment regimens in a randomized, double-blind, placebo controlled fashion, for a period of 6 weeks. Subjects will receive daily oral doses of either **2 mg micronized estradiol (Estrace®) plus placebo –OR– 200 mg micronized progesterone (Prometrium®) plus placebo.**

Rationale for preparation and dose of estrogen and progesterone. Natural estradiol is poorly absorbed in its native form and undergoes rapid metabolism in a first-pass effect through the liver. Thus, micronization (micronized estradiol) or acetylation (ethinyl estradiol) is required to achieve adequate blood hormone levels. Micronized estradiol is extremely well-absorbed and much of the compound is metabolized to estrone sulfate (65%) and estrone (15%). This “pool” of estrone and estrone sulfate then serves as the source of regenerated estradiol. At a dose of 2 mg per day, the steady-state levels of estradiol and estrone are typically 220 pmol/L and 68 pmol/L, respectively (116) and most closely recapitulate those seen in normal women in the midfollicular phase of the menstrual cycle (110). Because ethinyl estradiol is poorly converted to estrone, it will not be selected for use in these protocols. Micronized progesterone at a dose of 200 mg per day has been reported to result in attainment of serum progesterone concentrations typically seen in the late follicular/early luteal phase of the cycle (data provided by manufacturer).

Subjects randomized to Specific Aim 3 will be treated with nasal CPAP for a period of 6 weeks. Compliance will be documented based upon results provided by a microchip sensor that detects not only if the unit is powered on, but also if the mask is being worn by the subject. These data cannot be altered by the individual and there is no access to this microsensor by the user. The subjects who have OSA will undergo one night of CPAP titration study at the end of the baseline assessment. After 6 wks of home CPAP, the experimental study outline above will be repeated with CPAP use at night. Subjects whose average nightly CPAP use is > 5 hr will be considered compliant.

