Polysomnography results in a group of 17 PCOS women with OSA (defined by a total AHI  $\geq 10$ ) indicate that the mean AHI was  $18.4 \pm 8$  (Mean  $\pm$  SD). Using the SD from these preliminary data, for example, the present study would be powered to detect a difference of  $0.63 \times 8 = 5.04$  if the correlation is 0.75 (see **Table D3-1**). This would be equivalent to a mean change in AHI of 9.2 (a 50% decrease from baseline assuming a baseline level of 18.4) in the progesterone treated group versus a mean change of 4.2 (23% decrease from baseline assuming a baseline level of 18.4) in the estrogen treated group. The change in AHI ( $T_3 - T_1$ ) will be compared between the two groups using a two sample  $t$  test. This would amount to performing repeated measures analysis of variance on AHI and testing for group (progesterone vs. estrogen), time (pre- vs. post-treatment), and group by time interaction effects. The analysis will be performed both ways. Additionally, testosterone, estrogen, and progesterone levels at time T2 will be compared to the levels at T1 using a paired  $t$  test.

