**D4. Potential pitfalls and plans for their resolution**

re: Specific Aim 1. In studies conducted under Specific Aim 1, subjects will be recruited to participate in a wide variety of procedures over a number of weeks. Recruitment and retention may pose challenges, however we have longstanding experience with studies of this nature and our recruitment procedures have been successful to date; our retention rates in similar studies has been over 90%. Subjects are contacted on a regular basis by our study coordinator. Subjects also receive monetary compensation for participation in the protocols. We have successfully recruited subjects in the past through cooperation with other physicians who care for patients with PCOS and we plan to do so again in the event that recruitment goals are lagging.

re: Specific Aim 2. Studies in this Aim are anticipated to flow smoothly. Potential problems include drop-outs related to intolerance/untoward effects of study medication and lack of compliance. It is anticipated that additional subjects may need to be recruited to replace the drop-outs. Another potential pitfall is that the degree of testosterone suppression expected after depot-leuprolide administration may be insufficient (i.e., testosterone levels may remain above the normal female range). If this proves to be the case, we will use testosterone concentration as a covariate in our analyses related to metabolic changes pre- and post-leuprolide. Likewise, even though micronized estrogen and progesterone are optimized for oral absorption, if serum levels of estrogen and progesterone achieved are below the expected range observed in normal women, we will use these hormone concentrations as covariates in our statistical analyses. Although transdermal (patch or cream preparations) were an alternative to oral hormone therapy, the assessment of compliance with their use would have posed challenges. Pill counts, patient contact on a regular basis, and measurement of hormone levels in blood will be used to ensure and document use of study medication.

re: Specific Aim 3. This protocol requires high levels of commitment from study subjects who must use CPAP on a regular basis for the duration of the study. Compliance with CPAP use is automatically recorded and powering on the device can be differentiated from patient use via sensors incorporated into the CPAP mask. Thus, we will have device-generated compliance records.

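### Aim 2's between-arm AHI test is valid, but it uses a T3-T1 change score and ignores the AHI recorded at T2, before randomisation; ANCOVA on T1 and T2 would usually be more precise

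*Combined protocol and SAP*

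**What the plan says.** Section D3 (Statistical Considerations), Specific Aim 2, sets out the visits: "For this Aim, there are three time points of interest: baseline (T1), six weeks after administration of depot leuprolide (T2"), and T3 after six weeks of estrogen or progesterone. The between-arm analysis is: "The change in AHI ( $T_3 - T_1$ ) will be compared between the two groups using a two sample" t test. The plan notes that this amounts to a repeated measures ANOVA with time at two levels, pre and post, and says it will run both.

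Section D3 (Detail of methods pertaining to Specific Aims 2 and 3) describes the T2 visit: "subjects will return to the GCRC for repeated evaluation, identical to that conducted at Baseline under Specific Aim 1". The order of events is explicit: "After this midpoint assessment, subjects will again enter into a randomized phase of the protocol". T2 AHI is therefore measured before the estrogen/progesterone allocation.

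Section A, Specific Aim 2, gives T2 a purpose, "repeated assessment of metabolic, metabolomic, and sleep measures to determine if these outcomes are altered by the combined suppression of ovarian sex steroids", and adds: "Primary outcome measures will be compared both within and between treatment arms". In section D3 the only Aim 2 test that uses T2 concerns hormones: "testosterone, estrogen, and progesterone levels at time T2 will be compared to the levels at T1 using a paired" t test. Section D4 considers testosterone as a covariate only "in our analyses related to metabolic changes pre- and post-leuprolide", and achieved estrogen and progesterone levels if they fall short. Neither T1 nor T2 AHI is named as a covariate anywhere.

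**The concern.** Both arms receive leuprolide before they are randomised, so T3-T1 gives an unbiased comparison of estrogen with progesterone. The issue is precision, and it has two sources.

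- A change score forces the coefficient on T1 to be 1. ANCOVA estimates it. With equal SDs at both visits the true slope is r, so the forced value costs most when r is low.
- T2 AHI is a legitimate baseline covariate and the one closest in time to the outcome, yet neither form of the planned test uses it. Running the ANOVA as well adds nothing, because its group-by-time test is the same comparison.

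With 20 women per arm the primary comparison has little power to spare. The worked example reaches 80% only if r is 0.75, a value the documents do not support with data.

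There is a smaller gap. Section A raises two AHI questions: whether ovarian suppression alters sleep, and what happens within each arm. Section D3 names a test for neither. A within-arm change measured from T1, the defined baseline, would mix the leuprolide phase with the hormone phase.

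**Working it through.** **Inputs from section D3.** 20 per arm, two-sided alpha 0.05, 80% power, SD 8, r = 0.25, 0.50, 0.75 or 0.90, worked-example difference 0.63 × 8 = 5.04.

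**Assumed.** Equal SD at all visits and one common r for all three pairs of visits, unless stated otherwise.

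**Step 1: the plan's own table.** Detectable difference = (1.960 + 0.842) × √(2/20) × 8 × √(2(1−r)) = 0.8859 × 8 × √(2(1−r)). This gives 1.085, 0.886, 0.626 and 0.396 SD, against 1.08, 0.89, 0.63 and 0.40 in Table D3-1. The table reproduces.

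**Step 2: residual SDs.**

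- Change score: 8√(2(1−r)) = 9.80, 8.00, 5.66, 3.58
- ANCOVA on T1: 8√(1−r²) = 7.75, 6.93, 5.29, 3.49
- ANCOVA on T1 and T2: 8√(1−2r²/(1+r)) = 7.59, 6.53, 4.78, 3.07

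**Step 3: detectable differences.** Residual SD × 0.8859. The figures in brackets allow for estimating q slopes by multiplying the variance by 37/(37−q), that is 37/36 for one slope and 37/35 for two.

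| r | T3−T1 | ANCOVA on T1 | ANCOVA on T1 and T2 |
|---|---|---|---|
| 0.25 | 8.68 | 6.86 (6.96) | 6.72 (6.91) |
| 0.50 | 7.09 | 6.14 (6.22) | 5.79 (5.95) |
| 0.75 | 5.01 | 4.69 (4.75) | 4.24 (4.35) |
| 0.90 | 3.17 | 3.09 (3.13) | 2.72 (2.80) |

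At low r nearly all the gain comes from estimating the T1 slope. At high r most of it comes from T2.

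**Step 4: simulated power for a true difference of 5.04.** Normal data, 15,000 to 20,000 trials per case, t critical values, so the cost of estimating slopes is included.

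| Case | T3−T1 | T1 | T1 and T2 |
|---|---|---|---|
| Equal r = 0.25 | 36% | 51% | 51% |
| Equal r = 0.50 | 50% | 60% | 64% |
| Equal r = 0.75 | 78% | 83% | 88% |
| Equal r = 0.90 | 99% | 99% | >99% |
| r12 = r13 = 0.50, r23 = 0.75 | 50% | 60% | 83% |
| r12 = r13 = 0.75, r23 = 0.5625 | 78% | 82% | 81% |
| T1 SD 6, equal r = 0.75 | 83% | 82% | 88% |
| T1 SD 6, r12 = r13 = 0.75, r23 = 0.5625 | 84% | 83% | 81% |

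In the cases with r23 = 0.75 × 0.75 = 0.5625, T2 carries nothing beyond T1. In the cases with T1 SD 6, the true T1 slope is 0.75 × 8/6 = 1, so the change score is already the best analysis that uses T1 alone. Mean estimates were 5.02 to 5.06 for every method, so none is biased. A separate run of 5,000 trials per setting gave type I error of 4.4% to 5.6% for every method.

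**Step 5: the entry rule.** Section D2 requires AHI > 15, whereas the SD of 8 comes from women with AHI ≥ 10. Drawing T1 from a normal distribution with mean 18.4 and SD 8, keeping values above 15, with r = 0.75 before selection, gave 81/83/89% with equal correlations and 81/83/81% with T2 uninformative.

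**Step 6: missing T2.** At r = 0.75 with 4 of 40 T2 values missing at random (an assumed rate), power was 88% when T2 was filled in from T1 ignoring arm, 85% when those women were dropped, and 83% with T1 alone. Type I error with the fill-in rule was 5.1%.

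**The case against.** The strongest reply is that nothing here is an error. The planned test is unbiased, Table D3-1 reproduces, and the worked example reaches its stated power by the plan's own approximation. That is correct, and the point is put as an efficiency gain only.

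The second reply is that the T2 gain rests on correlations the documents do not give. Table D3-1 has a single pre/post r; equal r across three visits is an assumption. If T2 adds nothing beyond T1, including it costs about 1 point against ANCOVA on T1 alone (82% to 81%). This limits what can be said about size. The direction holds in most of the cases examined.

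Third, the entry rule narrows T1, so the benefit of adjusting for T1 is smaller than in unselected women: about 2 points at r = 0.75 in Step 5, rather than 4 to 5. This also stands. In another check of the same kind, at r = 0.90 with T2 uninformative and a difference of 3.2, ANCOVA on both lost about 1.5 points.

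Fourth, T2 AHI is not purposeless, because section A says why it is collected. Agreed: it is unused in the between-arm test, and the other AHI questions lack a named analysis. The detectable differences without brackets in Step 3 also omit the cost of estimating slopes; the bracketed ones and the simulated powers include it.

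**Conclusion.** The point holds as a low-cost improvement that should be made, not as a flaw in validity. ANCOVA of T3 AHI on arm, T1 and T2 is usually more precise than the T3-T1 comparison. At the plan's r = 0.75 with equal correlations, the detectable difference falls from 5.01 to 4.35 after the slope penalty, and power for 5.04 rises from 78% to 88%. At r = 0.50 power rises from 50% to 64%, or to 83% if T2 tracks T3 more closely than T1 does (r23 = 0.75). If T2 is uninformative and T1 has a narrow spread, about 2 points are lost. These figures rest on assumed inter-visit correlations, near-normal AHI and 20 women per arm. Confidence is high in the direction and lower in the size. The absence of a named within-arm or T2-T1 AHI analysis is a secondary gap in the specification.

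**What to change.** In section D3 (Statistical Considerations), Specific Aim 2:

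1. Make the primary between-arm analysis an ANCOVA of T3 AHI on randomised arm, with T1 and T2 AHI as prespecified covariates. Keep the T3-T1 t test as supportive.
2. State a rule for a missing T2 recording: replace it with the prediction from a regression of T2 on T1 fitted in both arms together, ignoring arm and T3, so that no woman with a T3 value is lost.
3. Name the AHI analyses that section A promises: T2-T1 in all 40 women, and T3-T2 within each arm. Report both as uncontrolled changes, outside the primary claim, and call neither a pure leuprolide or hormone effect.
4. As a clarification only, say what the polysomnography count of 1 in Table D1 means, since sections A and D3 plan repeat recordings.

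The cost is wording, two residual degrees of freedom (38 to 36) and the missing-T2 rule. No extra visit, recording or participant is needed. The text should be settled before unblinding, so that the covariates cannot be chosen with the result in view.
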